#### Research Data

The exploratory data derived from this study will be collected, analyzed and reported while the study is ongoing and with the approval of the Principal Investigator. The analyzed data will be reported and presented at institutional and scientific meetings and at invited presentations with the approval of the Principal Investigator. Use of the protocol data and publication of analyzed data is anticipated prior to completion of the study in the form of ongoing or preliminary reports and will be done only with approval of the Principal Investigator.

# 6.1 Physical Examination

e: St. Jude Children's Research Hospital

Physical examination will be performed before, during and after radiation therapy. The patient height, weight and body-mass index will be recorded and converted to percentiles based on age and gender.

# 6.2 **Neurology**

At baseline and with each visit the pediMIDAS form will be completed. Grade 3-5 neurological complications will be reported using the NCI Common Toxicity Criteria v4.0.

# 6.3 Ophthalmology

At the specified time points and when clinically indicated, patients will be assessed in the ophthalmology clinic. The ophthalmologic examination may consist of an assessment of external signs of treatment sequelae, visual acuity, current correction, color vision, intraocular pressure, mobility, refraction and visual field. The ophthalmology data sheet will no longer be collected in paper version. This data will be extracted directly from the patient's medical record clinical documentation and entered directly into the trial database.

# 6.4 Audiology

Schedule: Patients will be referred for audiological testing prior to radiation therapy and annually dated from the start of RT. More frequent evaluations may be considered by the treating physician or audiologist based on results of prior evaluations and the potential risk for hearing loss.

Tests and Outcome Measurements: At each evaluation tympanometry will be performed to assess integrity of the conductive mechanism, distortion product otoacoustic emissions will be assessed to determine cochlear outer hair cell function, a pure tone audiogram will be obtained to assess peripheral hearing sensitivity, and speech-in-noise testing will be administered to assess performance in background noise and to screen for auditory processing disorder in children. Each audiogram will include air conduction thresholds at 250, 500, 1000, 2000, 3000, 4000, 6000, and 8000 Hertz measured in dB HL. Ultra-high frequency thresholds will be obtained at 9000, 10000, 11200, 12500, 14000, and 16000 Hertz in patients older than 5 years. Bone conduction thresholds will be obtained as needed to rule out a conductive component to the hearing impairment. Hearing will be categorized as normal if all thresholds are within the 0-20 dB HL range. If a deficit is present, hearing impairment will be categorized by the numerical dB HL values. Speech-in-noise testing will be administered to patients older than 5 years. The QuickSIN speech-in-noise test [219] will be administered to patients older than 14 years and the BKB-SIN speech-in-noise test [220] will be used for patients 5-14 years and for adults whom the QuickSIN test is too difficult.

St. Jude Children's Research Hospital

IRB NUMBER: Pro00004349
IRB APPROVAL DATE: 02/01/2023

Rev. 3.2 dated: 1/19/2023

An auditory brainstem response (ABR) evaluation may be substituted for patients who are unable to respond to conventional audiometric testing techniques.

Every audiogram or ABR evaluation will be assigned a grade based on the Chang and SIOP Ototoxicity Grading Scales.

Ototoxicity Grading Scales\*

	Chang	SIOP					
Grade 0	$\leq$ 20 dB at 1, 2, and 4 kHz	Grade 0	≤20 dB HL at all frequencies				
Grade 1a	$\geq$ 40 dB at any freq 6 to 12 kHz		>20 dB HL (i.e., 25 dB HL or				
Grade 1b	> 20 and < 40 dB at 4kHz	Grade 1	greater) SNHL above 4000 Hz (i.e., 6 or 8 kHz)				
Grade 2a	≥ 40 dB at 4 kHz and above		>20 dB HL SNHL at 4000 Hz and				
Grade 2b	> 20 and < 40 dB at any freq below 4kHz	Grade 2	above				
Grade 3	≥ 40 dB at 2 or 3 kHz & above	Grade 3	>20 dB HL SNHL at 2000 Hz or 3000 Hz and above				
Grade 4	≥ 40 dB at 1 kHz and above	Grade 4	>40 dB HL (i.e., 45 dB HL or more) SNHL at 2000 Hz and above				

\*Sensorineural Hearing Threshold (dB HL) bone conduction or air conduction with normal tympanogram

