#### 1.2 Secondary Hypotheses and Secondary Objectives

Hypotheses: A second course of irradiation may be safely administered to patients with recurrent ependymoma after prior irradiation. The incidence and severity of side effects after second irradiation correlate with relevant clinical factors and treatment parameters, including radiation dose to normal tissue volumes and the use of chemotherapy before or after second irradiation. The selection of patients for re-irradiation can be improved by models that include clinical and treatment factors and longitudinal measures of CNS effects.

- 1.2.1 To explore potential associations of clinical and treatment factors with the incidence and severity of neurological, endocrine and cognitive deficits in children and young adults with ependymoma treated with a second course of irradiation
- 1.2.2 Using specific measures of sleep quality, excessive daytime sleepiness, daytime activity, fatigue, symptom distress, and quality of life, explore associations of sleep, fatigue and quality of life with other measures of CNS effects, clinical and treatment factors in children and young adults with ependymoma treated with a second course of irradiation.
- 1.2.3 To evaluate and explore differences in physical performance and movement in children and young adults with ependymoma treated with a second course of irradiation.
- 1.2.4 Estimate and compare the response of residual tumor and the incidence and severity of structural, physiological, and vascular effects of normal brain in children and young adults with ependymoma after treatment with a second course of irradiation using specific methods of diffusion, contrast-enhancement, magnetization transfer, vascular and functional

Rev. 3.2 dated: 1/19/2023 IRB Approval date: Protocol document date: 1/19/2023

St. Jude Children's Research Hospital

IRB NUMBER: Pro00004349

neuroimaging, and explore the association between these and other measures of CNS effects and clinical and treatment factors. Determine the time course of gray matter and white matter tract injury and recovery post irradiation and the association between imaging metrics derived from serial quantitative neural imaging and radiation dosimetry as well as neuro-cognitive outcomes.

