#### 5.12.1 Cochleae

- D50% < 3500cGy Goal (single cochlea)
- D50% < 2000cGy Preferred (single cochlea)
- Comment There is no dose limit for the cochleae.
- Structure definition Each cochlea will be contoured on the treatment planning CT as a circular structure within the petrous portion of the temporal bone. The contour should appear on at least two successive CT images.

IRB Approval date:

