also use the information recorded in the clinical neurology form (see appendix) and NCI CTCAE v4.0 when relevant. The percentages for both statuses will be estimated. Generalized Estimating Equations (GEE) with logistic link will be employed to estimate the change of vision over time, and compare severity of vision in the two treatment groups adjusted by confound factors.

**Audiology:** To assess hearing loss in patients, hearing will be dichotomized as normal if all thresholds are within 0-20 DB HL and otherwise abnormal. GEE with logistic link will be modeled to explore the trend over time and investigate impacts of specific clinical and treatment factors on hearing loss. In the presence of missing data, Weighted GEE will be employed to address missingness. In addition, the cumulative incidence of hearing loss will be estimated with death as a competing risk. Chang Ototoxicity Grading Scale (COGS) will also be used to evaluate the hearing loss. The ordinal COGS will be analyzed similarly as Neurology grade.

**Endocrine:** Endocrine data as a continuous variable will be collected. Descriptive statistical analysis will be performed. Diabetes Insipidus (DI) is a hormone deficiency that results only from direct damage to the hypothalamus and pituitary axis (mainly pituitary stalk) by tumor or surgery. This longitudinal binary variable (coded as "yes" or "no") will be compared between the surgery and radiation groups using GEE adjusted by other confounding factors. Hormone Deficiency, such as Growth Hormone Deficiency (GHD), will be compared between the surgery and radiation groups. Growth hormone will be dichotomized with GHD=1 for <7ng/ml and GHD=0, otherwise. We define GHD=1 as event. Since the treatment of other hormone deficiency could be a compete risk for this event, cumulative incidence regression analysis using Fine and Gary method will be employed [301]. Specific clinical and treatment group factors will be included as covariates to investigate the treatment group difference. Other Hormone Deficiency, including Thyroid Hormone Deficiency (central hypothyroidism), Adrenal Insufficiency, Gonadotropin Deficiency or Precocious Puberty, Diabetes Insipidus, Hypothalamic Obesity (not a specific endocrine deficiency but an endocrine problem nonetheless), will be analyzed similarly. Some of these measures are graded in the NCI CTCAE v4.0.

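### Hearing has no ear-level unit although cochlear dose is handled per ear, so second-ear loss cannot show in the binary outcome and the dose-hearing analysis loses information

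*Combined protocol and SAP*

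**What the plan says.** **Outcome.** Section 6.4 lists what is measured: "Each audiogram will include air conduction thresholds at 250, 500, 1000, 2000, 3000, 4000, 6000, and 8000 Hertz measured in dB HL". No ear is mentioned. The rule for status is "Hearing will be categorized as normal if all thresholds are within the 0-20 dB HL range", and the grading rule is "Every audiogram or ABR evaluation will be assigned a grade based on the Chang and SIOP Ototoxicity Grading Scales".

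Section 11.2 (Audiology) carries this into the analysis: "To assess hearing loss in patients, hearing will be dichotomized as normal if all thresholds are within 0-20 DB HL and otherwise abnormal". The binary status goes into a longitudinal model: "GEE with logistic link will be modeled to explore the trend over time and investigate impacts of specific clinical and treatment factors on hearing loss". A time-to-event summary is also planned: "the cumulative incidence of hearing loss will be estimated with death as a competing risk". The ordinal Chang grade is to be analysed in the same way as the neurology grade. The section gives no better-ear or worse-ear rule, no clustering of ears within patient, and no at-risk set for the incidence estimate.

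**Exposure.** Section 5.12.1 is ear-specific: "Each cochlea will be contoured on the treatment planning CT", and its D50 goals are stated for one cochlea. Section 5.13.2 requires separate right and left cochlea DVHs.

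**Question.** The secondary hypothesis in section 1.2 is that side effects "correlate with relevant clinical factors and treatment parameters, including radiation dose to normal tissue volumes". Section 1.4.2 counts all radiation planning and delivery parameters as treatment factors, so cochlear dose falls within Objective 1.2.1 by implication. Section 11.2 does not name it as a covariate.

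**The concern.** The exposure comes in pairs and the outcome does not. A patient-level status has to be set against some summary of two cochlear doses, and the comparison between a patient's higher-dose and lower-dose ear is not used.

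One-sided loss at entry is plausible here. Every patient has already been irradiated, section 2.2 lists transient and permanent hearing damage among the deficits, and section 4.2 mentions residual tumor in the internal auditory meatus. For such a patient, loss in the remaining good ear matters most for function, and the binary outcome cannot register it. With no combination rule, two analysts could also grade the same asymmetric audiogram differently.

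**Working it through.** The documents give no hearing rate, cochlear dose distribution, between-ear correlation or power for hearing. There is therefore no figure to reproduce, and every input below not attributed to the documents is assumed.

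**1. What the stated rule does.** If normal means that all of a patient's thresholds are within range, the status is the any-ear maximum. Once one ear is abnormal, the maximum is fixed and a change in the other ear cannot alter it. The same holds for the incidence curve: such a patient is either not at risk or already counted. This step needs no simulation.

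**2. How much the binary outcome can miss.** Let p be the probability that an ear is affected and rho the between-ear correlation.
- P(both) = p² + rho·p(1−p)
- P(any) = 2p − P(both)
- Share of affected patients with both ears affected = P(both)/P(any)
- Share of affected ears not counted separately = P(both)/(2p)

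At p = 0.1, rho = 0: P(both) = 0.01 and P(any) = 0.19, giving shares of 5% and 5%. At p = 0.4, rho = 0.6: P(both) = 0.16 + 0.144 = 0.304 and P(any) = 0.496, giving 61% and 38%. Other values in this grid lie between.

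For loss already present at entry, a separate simulation put about 15% of new ear losses in patients already coded abnormal when 15% of ears were affected at baseline, and 26% when 25% were. That is close to the baseline rate itself, as expected if the two ears are nearly independent.

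**3. Is the dose coefficient attenuated?** Assumed model: ear-level logit = −1.4 + 0.7 × dose (per SD) + patient effect (SD 1), with about 25% of ears affected and between-ear dose correlation from 0 to 0.9. Large-sample log odds ratios per SD of a single ear's dose were:
- ear-level: about 0.60
- any-ear on mean dose: 0.63-0.65
- any-ear on maximum dose: 0.52-0.64
- any-ear on one ear's dose: 0.30-0.61

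There is no attenuation on mean dose, some on maximum dose when the ears differ, and up to about half on one ear's dose.

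**4. Power.** Same model, n = 90 (the required number of eligible patients), one time point, two-sided 0.05, 600 replicates:

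| Between-ear dose correlation | Ear-level GEE | Any-ear, mean dose | Any-ear, maximum dose | Ratio |
|---|---|---|---|---|
| 0 | 0.91 | 0.52 | 0.46 | 1.8-2.0 |
| 0.3 | 0.89 | 0.60 | 0.55 | 1.5-1.6 |
| 0.6 | 0.91 | 0.70 | 0.68 | 1.3 |
| 0.9 | 0.88 | 0.78 | 0.77 | 1.1 |

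If only one ear's dose were used, the ratio would run from 0.91/0.28 = 3.3 at correlation 0 to 0.88/0.76 = 1.2 at correlation 0.9.

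A second model used n = 60, mean D50 22 Gy, SD 12, between-ear correlation 0.3 and odds ratio 1.05 per Gy. It gave 39% against 19-21%, a ratio of about 1.9-2.1. Its patient-level comparator was limited to patients with two normal ears, and type I error was 7% against 3%, so part of that gap is not a real gain.

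**5. Craniospinal patients.** In Table 11.0, 7 + 16 + 5 = 28 of 50 historical patients (56%) received craniospinal irradiation. Assume about 37 Gy to both cochleae for them and, for focal patients, mean 15, SD 12 and correlation 0.3.
- Between-group variance: 0.56 × 0.44 × 22² = 119.3
- Focal variance: 0.44 × 144 = 63.4
- Focal covariance: 0.44 × 0.3 × 144 = 19.0
- Pooled correlation: (119.3 + 19.0)/(119.3 + 63.4) = about 0.76

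One run with this mixture at n = 60 gave 65% against 43-47% (ratio 1.4-1.5). In the same run with a common correlation of 0.3 it was 58% against 26-28% (2.1-2.2). Another run, also 56% craniospinal with near-equal ear doses and without the restriction to two normal ears, gave 0.64 against 0.36 at n = 60 (1.8) and 0.84 against 0.53-0.57 at n = 90 (1.5-1.6). Type I error in that run was 0.02-0.06.

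**The case against.** **Silence is not a design choice.** The documents never say that the two ears are merged, and they do not say that thresholds are stored per ear. Both are inferences: the first from the all-thresholds rule and the absence of an ear, the second from how audiometry is normally done. This stands, and the point is limited to what follows if the rule is applied as written.

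**A diluted dose effect.** A reader might infer that the cochlear-dose association will be biased towards zero. The documents do not support that. Section 11.2 specifies no cochlear-dose model, and with mean dose the coefficient is not attenuated. Loss of information is the most that can be said.

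**Doubled power.** A reader might also expect ear-level analysis to double the power. That depends on asymmetric doses, and the advantage shrinks as the two cochlear doses become alike.

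**Other hearing outcomes.** The Chang grade is analysed too, and a second-ear loss that raises the grade would show there. This stands in part. The grade is one per evaluation with no stated ear; if it is read as the worse ear, change in the better ear is hidden until it passes the worse one.

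**Cost and standing.** Audiograms already obtained would need regrading, and 53 patients had been accrued by amendment 2 (section 11.1). Section 4.1 accepts hard-copy records of the first course, so composite cochlear dose may not be computable for everyone. Objective 1.2.1 is exploratory with no power claim for hearing. All of this stands and sets the weight of the point.

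**Conclusion.** The concern holds in a limited form. The plan defines neither the ear as a unit nor a rule for combining ears, while cochlear dose is ear-specific. Under the all-thresholds rule, second-ear loss cannot enter the binary GEE or the cumulative incidence; this follows by logic. How often it happens is not known from the documents: over 10-40% of ears affected and between-ear correlation 0-0.6, 5% to 38% of affected ears would not be counted separately.

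For the dose question, ear-level analysis had higher power in every scenario tried. The ratio was roughly 1.1 to 2.2 against mean or maximum dose in the matched comparisons, nearest 1 when the two cochlear doses are almost equal. These figures are illustrative; the direction is better supported than the size.

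A reader might go further and doubt the trial's main conclusions. Nothing here supports that: PFS, OS, the necrosis stopping rule and the sample size do not depend on hearing. The point is a cheap improvement to a secondary exploratory analysis.

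**What to change.** **Section 6.4.** Record the normal/abnormal status, the Chang grade and the SIOP grade for each ear at every evaluation.

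**Section 11.2.**
- Make the ear the unit of analysis, with ears and visits clustered on patient: logistic GEE for the binary status, a mixed model for the ordinal grade.
- Use same-side cochlear dose as the covariate: composite over both courses where prior dosimetry allows, otherwise the current-course D50 from the DVH already required.
- Include that ear's pre-irradiation status as a covariate.
- Estimate cumulative incidence among ears normal at baseline, with death as the competing risk and clustering respected.
- Keep worse-ear and better-ear patient status as descriptive summaries, with the rule for each stated.

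**Cost.** This means SAP wording plus six fields per evaluation (three items × two ears) instead of three. Existing audiograms must be regraded, which is possible only if the source records hold thresholds by ear; that should be confirmed first. Composite dose will be missing for some patients, so the report should say how many rely on current-course dose alone. GEE is already the planned method and the right and left DVHs are already required.

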# 6.5 Endocrinology

To establish a baseline, patients will be evaluated for evidence of endocrinopathy and abnormal growth and development. They will be seen by the endocrine service at baseline and then at least once annually to document their developmental exam and to perform auxological measurements.

When necessary, the baseline and follow-up developmental exam and auxological measurements may be performed by a trained co-investigator.

Endocrine Imaging: Baseline evaluation will include 1) a plain film posteroanterior X-ray of the left hand and wrist for bone age; 2) quantitative CT; and 3) DXA scan for bone mineral density for participants  $\geq$  3 years of age. These examinations will be repeated when deemed necessary by the treating physicians.

Serum Screening Studies: Hypothalamic-pituitary axis function will be assessed with static assessments of fasting serum: thyrotropin (TSH), free and total thyroxine [212], reverse and total T3, cortisol (obtained by 0800 hours), prolactin, insulin-like growth factor binding protein-1 (IGFBP-1, marker of insulin resistance) and insulin-like growth factor binding protein-3 (IGFBP-3), IGF-1, LH, FSH, insulin, 25(OH)D, serum Comprehensive Metabolic Panel (CMP) and complete blood count. These evaluations will be performed with each planned follow-up. These screening tests resemble those drawn for routine evaluation.

IRB Approval date:

Rev. 3.2 dated: 1/19/2023 Protocol document date: 1/19/2023 St. Jude Children's Research Hospital

IRB NUMBER: Pro00004349

Understanding the pan-endocrine status is critical to interpretation of the GH data from the provocative testing.

Provocative Endocrine Testing: Patients will undergo evaluation for growth hormone and ACTH secretion abnormality using provocative tests of endocrine function. Recent steroid or growth hormone usage by the patient will be reviewed by the PI to determine when and if provocative endocrine testing shall be performed. GH provocative testing will be performed using arginine and carbidopa-levodopa. ACTH secretion will be tested using the 1 µg ACTH test. Similar evaluations will be repeated at 12 and 24 months after irradiation. The protocols used for provocative testing are identical to those used for patients in whom endocrinopathy is suspected. Exceptions to the endocrine testing procedures may be made at the discretion the treating physicians. Testing procedures may be omitted or modified: 1) because the patient is receiving replacement therapy; 2) when the provocative agent is unavailable; or 3) when the procedure is deemed inappropriate based on patient's clinical condition, 4) the intraday timing of the drug administration, or 5) phlebotomy is constrained by logistic problems.

#### 6.6 **Neuropsychological Testing**

## 6.6.1 Overview of Neurocognitive Studies – Schedule

Patients will be referred for neurocognitive testing before radiation therapy and yearly through 5 years. All measures in the battery described below will be administered at yearly time points with the exception of the CVLT-C/CVLT-II, which will be administered only at baseline, 2 years post radiation therapy and 4 years post radiation therapy in order to minimize practice effects. We will not perform cognitive assessments on children less than 3 years of age, children for whom a language other than English is their primary language, or children with premorbid neurological/neurodevelopmental disorders (e.g., Down Syndrome, Autism).

#### **6.6.2** Neurocognitive Testing

Children will be assessed at baseline (pre re-irradiation therapy and up to 4 months after the initiation of treatment) and annually for 5 years. An effort was made to select measures that could assess the widest study age range possible. Another primary goal was to select a battery that could be administered in a circumscribed period of time to reduce the time burden for children, their parents and the research team. The administration time for the test battery is estimated at 2-3 hours, dependent on the age of the child and the speed with which they can complete tasks. Therefore, the administration length of the current battery readily lies within the standard length of typical clinical and research batteries. All selected measures have age-specific norms from large, representative standardization samples. Measures also have appropriately demonstrated reliability and validity. Given the longitudinal study design, measures were

Rev. 3.2 dated: 1/19/2023 IRB Approval date: IRB NUMBER: Pro00004349 Protocol document date: 1/19/2023

St. Jude Children's Research Hospital

chosen with appropriate test-retest reliability and negligible practice effects for the proposed interval between testing time points. Tasks were chosen that balance the need to measure global outcomes typically assessed with respect to treatment interventions and most useful for educational planning (e.g., IQ and academic achievement) with specific areas of deficit most commonly reported in the brain tumor literature for children receiving radiation therapy (e.g., attention, processing speed and executive functions). See Table 1 for a listing of measures by cognitive domain.

